13 SAFETY MONITORING AND REPORTING

The PI is responsible for the identification and documentation of adverse events and serious adverse events, as defined below. At each study visit, the PI or designee must assess, through non-suggestive inquiries of the subject or evaluation of study assessments, whether an AE or SAE has occurred.

13.1 Adverse Events

An AE is any untoward medical occurrence in a subject receiving study drug and which does not necessarily have a causal relationship with this treatment. For this protocol, the definition of AE also includes worsening of any pre-existing medical condition. An AE can therefore be any unfavorable and unintended or worsening sign (including an abnormal laboratory finding), symptom, or disease temporally associated with the use of the PEP_{IDH1M} and GM-CSF, whether or not related to use of the vaccine. Abnormal laboratory findings without clinical significance (based on the PI's judgment) should not be

recorded as AEs. But laboratory value changes that require therapy or adjustment in therapy are considered adverse events. All lab values that are not deemed AEs by the PI will be noted to be Non-Clinically Significant in the subject record and source documents.

From the time the subject signs the informed consent form through the End of Treatment visit (as defined in Sections 12.3, 12.5 and 12.6), all AEs must be recorded in the subject medical record and electronic adverse events case report form.

AEs will be assessed according to the CTCAE version 4.0. If CTCAE grading does not exist for an AE, the severity of the AE will be graded as mild (1), moderate (2), severe (3), life-threatening (4), or fatal (5). Attribution of AEs will be indicated as follows:

- Definite: The AE is clearly related to the study drug
- Probably: The AE is likely related to the study drug
- Possible: The AE may be related to the study drug
- Unlikely: The AE is doubtfully related to the study drug
- Unrelated: The AE is clearly NOT related to the study drug

13.1.1 Reporting of AEs

A summary of all adverse events (not just those considered related to the study drug) will be kept which will categorize the event by organ system, relationship to treatment, its grade of severity, and resolution. The PI will periodically review the collective adverse events with the intention of identifying any trends or patterns in toxicity on a monthly basis. If any such trends are identified, depending on their severity and frequency, a protocol amendment will be considered.

13.2 Serious Adverse Events

An AE is considered "serious" if in the opinion of the investigator it is one of the following outcomes:

- Death,
- A life-threatening adverse event,
- A congenital anomaly or birth defect,
- Inpatient hospitalization or prolongation of existing hospitalization,
- A persistent or significant incapacity or substantial disruption in the ability to conduct normal life functions.

Important medical events that may not result in death, be life-threatening, or require hospitalization may be considered serious when, based upon appropriate medical judgement, the event may jeopardize the subject and may require medical or surgical intervention to prevent one of the outcomes listed in this definition. Furthermore, an important medical event that is not otherwise an SAE may be considered serious if the event may jeopardize the subject and may require medical or surgical intervention to prevent one of the outcomes listed in the outcomes listed in this definition.

13.2.1 Reporting of SAEs

All SAEs should be reported immediately to [name] ([contact]) or her designee [contact]) and to the FDA. Fatal or life-threatening, unexpected adverse events will be reported to the FDA by telephone, facsimile, or in writing as soon as possible, but no later than 7 calendar days after first knowledge by the PI-sponsor followed by as complete a report as possible within 8 additional calendar days. Serious, unexpected adverse events that are not fatal or life-threatening will be reported to the FDA by telephone, facsimile, or in writing as soon as possible, but no later than 15 calendar days after first knowledge by the sponsor.

All adverse events that are considered serious, unanticipated, and related or possibly related to the research (as defined by 21CRF312.32[a]) will be reported to the FDA and the Duke University Medical Center IRB using the appropriate SAE report form. At the time of the annual progress report to the FDA and the Duke University Medical Center IRB, a summary of the overall toxicity experience will be provided.

13.3 Safety Oversight Committee

The Duke Cancer Institute Safety Oversight Committee is responsible for annual data and safety monitoring of DUHS sponsor-investigator phase I and II, therapeutic interventional studies that do not have an independent DSMB. The primary focus of the Safety Oversight Committee is review of safety data,

toxicities and new information that may affect subject safety or efficacy. Annual safety reviews includes but may not be limited to review of safety data, enrollment status, stopping rules if applicable, accrual, toxicities, reference literature, and interim analyses as provided by the sponsor-investigator. The Safety Oversight Committee in concert with the DCI Monitoring Team (see Section 14.1 for Monitoring Team description) oversees the conduct of DUHS cancer-related, sponsor-investigator therapeutic intervention and prevention intervention studies that do not have an external monitoring plan, ensuring subject safety and that the protocol is conducted, recorded and reported in accordance with the protocol, SOPs, GCP, and applicable regulatory requirements.

14 QUALITY CONTROL AND QUALITY ASSURANCE

14.1 Monitoring

The DCI Monitoring Team will conduct monitoring visits to ensure subject safety and to ensure that the protocol is conducted, recorded, and reported in accordance with the protocol, standard operating procedures, good clinical practice, and applicable regulatory requirements. As specified in the DCI Data and Safety Monitoring Plan, the DCI Monitoring Team will conduct routine monitoring after the third subject is enrolled, followed by annual monitoring of 1–3 subjects until the study is closed to enrollment and subjects are no longer receiving study interventions that are more than minimal risk.

Additional monitoring may be prompted by findings from monitoring visits, unexpected frequency of serious and/or unexpected toxicities, or other concerns and may be initiated upon request of DUHS and DCI leadership, the DCI Cancer Protocol Committee, the Safety Oversight Committee, the sponsor, the Principal Investigator, or the IRB. All study documents must be made available upon request to the DCI Monitoring Team and other authorized regulatory authorities, including but not limited to the National Institute of Health, National Cancer Institute, and the FDA. Every reasonable effort will be made to maintain confidentiality during study monitoring.

14.2 Audits

The Duke School of Medicine Office of Audits, Risk, and Compliance (OARC) office may conduct audits to evaluate compliance with the protocol and the principles of GCP. The PI agrees to allow the OARC auditor(s) direct access to all relevant documents and to allocate his/her time and the time of the study team to the OARC auditor(s) in order to discuss findings and any relevant issues.

OARC audits are designed to protect the rights and well-being of human research subjects. OARC audits may be routine or directed (for cause). Routine audits are selected based upon risk metrics generally geared towards high subject enrollment, studies with limited oversight or monitoring, Investigator initiated Investigational Drugs or Devices, federally-funded studies, high degree of risk (based upon adverse events, type of study, or vulnerable populations), Phase I studies, or studies that involve Medicare populations. Directed audits occur at the directive of the IRB or an authorized Institutional Official.

OARC audits examine research studies/clinical trials methodology, processes and systems to assess whether the research is conducted according to the protocol approved by the DUHS IRB. The primary purpose of the audit/review is to verify that the standards for safety of human subjects in clinical trials and the quality of data produced by the clinical trial research are met. The audit/review will serve as a quality assurance measure, internal to the institution. Additional goals of such audits are to detect both random and systemic errors occurring during the conduct of clinical research and to emphasize "best practices" in the research/clinical trials environment.

14.3 Data Management and Processing

14.3.1 Study Documentation

Study documentation includes but is not limited to source documents, case report forms, monitoring logs, appointment schedules, study team correspondence with sponsors or regulatory bodies/committees, and regulatory documents that can be found in the DCI-mandated "Regulatory Binder," which includes but is not limited to signed protocol and amendments, approved and signed informed consent forms, FDA Form 1572, CAP and CLIA laboratory certifications, and clinical supplies receipts and distribution records.

Source documents are original records that contain source data, which is all information in original records of clinical findings, observations, or other activities in a clinical trial necessary for the reconstruction and evaluation of the trial. Source documents include but are not limited to hospital records, clinical and office charts, laboratory notes, memoranda, subjects' diaries or evaluation checklists, pharmacy dispensing records, recorded data from automated instruments, copies or transcriptions certified after verification as being accurate copies, microfiches, photographic negatives, microfilm or magnetic media, x-rays, subject files, and records kept at the pharmacy, at the laboratories and at medico-technical departments involved in the clinical trial. When possible, the original record should be retained as the source document. However, a photocopy is acceptable provided that it is a clear, legible, and an exact duplication of the original document.

14.3.2 Data Management

The subject's medical records will be the primary source document for the study. Source documents include all information in original records and certified copies of original records of clinical findings, observations, or other activities in a clinical investigation used for reconstructing and evaluating the investigation¹. Source documentations may also include paper eligibility checklists, data flowsheets, patient reported outcomes and other paper documents. The PI, study coordinator, study research nurse, data management team and all associated study key personnel, are permitted to make entries, changes, or corrections in the source documents or database per the study delegation of authority log.

Errors on the source documents will be crossed out with a single line, and this line will not obscure the original entry. Changes or corrections will be dated, signed, initialed, and explained (if necessary). Database changes will be tracked via electronic trail automatically.

14.3.3 Data Management and Data Verification

The DCI IT Shared Resource has developed Title 21 CFR Part 11 compliant databases for cancer clinical trials. DCI IT has extensive expertise in database quality assurance, data standards, and use of caBIG tools to support cancer researchers.

Data queries will be generated automatically by the eCRF system. These data queries signify the presence of data inconsistencies. The study and data management team will cross-reference the data to verify accuracy. Missing or implausible data will be highlighted for the PI requiring appropriate responses (i.e. confirmation of data, correction of data, completion or confirmation that data is not available, etc.).

The database will be reviewed and discussed prior to database closure, and will be closed only after resolution of all remaining queries.

14.3.4 Coding of Adverse Events

All adverse events will be coded using CTCAE (version 4.0).

14.3.5 Study Closure

Following completion of the studies, the PI will be responsible for ensuring the following activities:

- Data clarification and/or resolution
- Accounting, reconciliation, and destruction/return of used and unused study drugs
- Review of site study records for completeness
- Shipment of all remaining laboratory samples to the designated laboratories

¹ In 21 CFR 312.62(b), reference is made to records that are part of case histories as "supporting data"; the ICH guidance for industry *E6 Good Clinical Practice: Consolidated Guidance* (the ICH E6 guidance) (available at http://www.fda.gov/Drugs/GuidanceComplianceRegulatoryInformation/Guidances/default.htm or http://www.fda.gov/Drugs/GuidanceComplianceRegulatoryInformation/Guidances/default.htm) uses the term "source data/documents." For the purpose of this guidance, these terms describe the same information and have been used interchangeably.

15 STATISTICAL METHODS AND DATA ANALYSIS

All statistical analyses will be performed under the direction of the statistician designated in key personnel. Any data analysis carried out independently by the investigator must be approved by the statistician before publication or presentation.

15.1 Analysis Sets

Subject to the availability of data, all patients who receive any protocol treatment will be included in analyses addressing secondary objectives. Statistical analyses for the primary objective will exclude patients who terminate protocol treatment prematurely (i.e. less than 6 vaccinations) without an unacceptable toxicity.

15.2 Patient Demographics and Other Baseline Characteristics

Summaries of clinical and socio-demographic characteristics will be generated for all patients who receive vaccine treatment. Categorical descriptors will be summarized using frequency distributions; whereas, interval variables will be summarized using percentiles, as well as means and standard deviations.

15.3 Treatments

A frequency distribution will be generated for the number of vaccines received by patients.

15.4 **Primary Objective**

To assess the safety of the PEP_{IDH1M} vaccine alone and in combination with adjuvant TMZ and/or RT in adult patients with progressive, resectable WHO Grade II gliomas that are confirmed Grade II or transition to a higher grade glioma at the time of surgery.

15.4.1 Variable

The percentage of patients with an unacceptable toxicity will be estimated, where unacceptable toxicity is defined as any Grade 3 toxicity at least possibly attributed to the vaccine (or vaccine + TMZ and/or RT) that does not resolve to baseline within 3 weeks, any Grade 3 hypersensitivity reactions requiring steroids, any Grade 4 toxicity, including neurologic events not due to progressive disease, or any life threatening-event not attributable to concomitant medication, co-morbid event, or disease progression.

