All Adverse Events will be collected from time of consent until the end of the treatment phase of the study. The treatment phase of the study will end 1 month after the last vaccine (Section 12.3). Patients will be followed only for overall survival, progression-free survival, and subsequent therapies thereafter. For higher grade gliomas undergoing RT (please see Section 18.4 in the Appendices for SOC RT), vaccine #4 will be given during the SOC clinic visit prior to initiating RT, and vaccine # 5 will be given 4 weeks later (± 1 week) during RT. Vaccine #6 will be given at the end of RT during the SOC clinic visit to review MRI and begin post-RT TMZ, if MRI stable. Then, subjects in this treatment group will receive vaccines monthly on day 22 (+2 days) with post-RT cycles of TMZ to a maximum of 15 vaccines.

For immune monitoring and biomarker testing, subjects will have blood collected, as described in Section 12, during the following times: prior to vaccine therapy (at leukapheresis visit), prior to surgical resection (at the pre-op screening visit), prior to either RT/TMZ or first cycle of adjuvant TMZ (at SOC clinic visit) depending on tumor pathology, at vaccine # 6, and at End of Treatment (follow-up visit 1 month after vaccine #15; If a subject decides to stop participating in the study prior to vaccine #15, blood will be obtained at that time, if possible; If a subject progresses prior to vaccine #15, blood will be obtained at that time, if possible). For genomic proteomic analyses, blood and tumor samples will be obtained as described below in Section 9.4.

Subjects will be imaged with contrast-enhanced MRI according to the SOC every 10 weeks (+/- 4 weeks) while on TMZ and afterward, per the treating neuro-oncologist's recommendation. RANO criteria will be used for assessment of pseudoprogression and tumor progression (please see Section 12.7.3 for further detail). Subjects demonstrating definitive progression will be removed from study.

In addition, to demonstrate quantitative repeatable measures of 2HG in IDH1+ gliomas, subjects will be imaged using magnetic resonance spectroscopy (MRS) at baseline (prior to vaccine #1 following consent), and up to 4 times prior to surgery (please see Section 9.5 below for further information).

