12.8.2 Potential Risks

Td

Injection of Td toxoid may produce inflammation, edema, induration, erythema, or pruritus at the injection site. Administration may cause occasional pain and discomfort up to three days after the vaccine is given.

Allergic Reactions to PEPIDH1M

Injection of antigen presenting cells may result in an allergic reaction, which could include redness and swelling at the injection site, itching, hives, low blood pressure, difficulty breathing, or in the most extreme circumstances, death. In addition, if the immune system becomes overly activated, potential discomforts may include pain, redness and swelling at the injection site.

Injection Site

EMLA ® cream, or equivalent topical analgesic, can be offered to subjects who experience local pain at the injection site.

Cerebral Edema

Cerebral edema may be secondary to the disease process itself, the surgical procedure, radiation therapy, necrosis from previous radiation, or inflammation due to immune infiltration of the brain or destruction of tumor cells. Symptoms may include, but are not limited to, severe headache, confusion,

lethargy, unresponsiveness, coma, or focal neurological deficits. Patients will be monitored throughout the course of the study and those patients with any signs or symptoms of cerebral edema may need their steroid doses increased, treatment with an osmotic diuretic, or surgical decompression. Edema that fails to respond to aggressive therapy may lead to permanent neurological impairment. The probability of this risk can be predicted to some degree based upon tumor size, location, pre-operative neurological impairment, and post-operative course prior and after PEP_{IDH1M} injections. Patients will be monitored throughout the course of the study.

Infection

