Drawing blood or inserting an intravenous catheter into an arm vein may result in bruising or swelling in the area of the insertion, bleeding at the site of the needle puncture, light headedness, fainting and very rarely, local infection, which may be severe. These risks are reduced by the fact that the blood will be drawn by a qualified physician, nurse or phlebotomist (a professional trained to draw blood).

Leukapheresis

As with any donation of blood, a variety of minor reactions may occur with leukapharesis, which include fainting, dizziness, or nausea. Uncommon but serious complications may also result, which include bleeding, infection, an adverse reaction to the anticoagulant or replacement fluids, hypocalcemia, hypotension, shock, convulsions, air emboli, heart failure, or the inability to transfuse blood back into the patient. These risks are reduced by the fact that the procedure will be performed by qualified staff at a specialized clinical hemapheresis unit. Patients will be carefully monitored throughout the procedure by trained nursing and medical staff. Calcium gluconate (2 gm) will be given to minimize the risks of hypocalcemia, fluid supplementation will be given to minimize hypotension.

MRI

The risks and/or discomforts associated with the performance of MRI include the anxiety produced from being in a tight, enclosed space (claustrophobia). In addition, the machine operates using a large and powerful magnet. The magnetism of the machine attracts certain metals: therefore, people with these metals in their bodies (specifically pacemakers, infusion pumps, metal aneurysm clips, metal prostheses, joints, rods or plates) will be excluded from the study if they are unable to undergo MRI imaging. Patients will also be checked to make sure that they do not bring any metal objects into the MRI facility. Dental fillings are less affected by the magnetic fields generated and are therefore permitted. It will be asked that patients let the physicians conducting this study know of any metal in their bodies other than dental fillings.

Allergic Reactions to Contrast Agents

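### The Grade 4 part of the primary endpoint has no attribution test, Section 9.6 conflicts with Sections 15.1 and 15.4.2 on relatedness, and attribution is scaled to the vaccine only

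*Combined protocol and SAP*

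**What the plan says.** Section 15.4.1, repeated in substance in Sections 8 and 9.1.1, builds unacceptable toxicity from several limbs. Three matter here:

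- Grade 3: the event must be "at least possibly attributed to the vaccine (or vaccine + TMZ and/or RT) that does not resolve to baseline" within three weeks.
- Grade 4: "any Grade 4 toxicity, including neurologic events not due to progressive disease".
- Life-threatening: "any life threatening-event not attributable to concomitant medication, co-morbid event, or disease progression".

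Section 9.1 states the collection window: "All Adverse Events will be collected from time of consent until the end of the treatment phase of the study". Table 2 marks AE collection at leukapheresis and at surgery. Section 12.8.2 names non-vaccine causes of serious events. On edema it says "Cerebral edema may be secondary to the disease process itself, the surgical procedure, radiation therapy, necrosis from previous radiation", and on leukapheresis "Uncommon but serious complications may also result, which include bleeding, infection".

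Section 13.1 gives five attribution categories, all relative to one agent, for example "Possible: The AE may be related to the study drug". Section 10.1 names that agent as the peptide vaccine. Section 13.1.1 adds a single relationship-to-treatment entry in the AE summary, not split by component.

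Three sections say who enters the primary analysis. Section 9.6 admits patients with at least six vaccinations, or with an unacceptable event related to vaccine or to vaccine plus TMZ. Sections 15.1 and 15.4.2 admit a patient with fewer than six vaccinations who had any unacceptable toxicity. Section 15.4.3 drops patients who were never vaccinated.

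**The concern.** Every patient is scheduled for leukapheresis before vaccine #1 and for a standard-of-care resection 7 to 12 days after vaccine #3. A Grade 4 complication of the resection meets the Grade 4 limb on its wording, even if the investigator is certain that the vaccine played no part. It would then enter both the primary percentage and the Table 3 count.

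For Grade 3 the problem is different. The endpoint refers to vaccine with TMZ and/or RT, but the specified scale asks only about the vaccine. Section 15.4.2 nevertheless expects toxicities attributable to either TMZ or vaccine, and it benchmarks the suspension rule to an 18% Grade 3 or 4 rate on TMZ alone.

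The percentage of patients with unacceptable toxicity is the only primary variable, and the same definition drives accrual suspension. If the text does not fix which events count, two analysts could obtain different primary results from the same data.

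**Working it through.** **1. The limbs side by side.** Grade 3 has an attribution test. The life-threatening limb has a list of excluded causes. Grade 4 has only the progression exception for neurologic events. On the fallback severity scale in Section 13.1, grade 4 means life-threatening. A Grade 4 event due to comorbidity or another drug can therefore be counted by the Grade 4 limb and excluded by the life-threatening limb.

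**2. Who is counted.** Take a vaccinated patient with a Grade 4 post-craniotomy complication judged unrelated to vaccine and TMZ.

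- Reaches six vaccines: evaluable under all sections, and the event counts.
- Stops before six: outside the analysis under 9.6, but in both numerator and denominator under 15.1 and 15.4.2.

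The second case is realistic, because Section 12.6.1 lists unacceptable toxicity among possible reasons for withdrawal. With 20 completers of whom k have an event, one such patient changes the estimate from k/20 to (k+1)/21. For an illustrative k = 3, that is 3/20 = 15.0% against 4/21 = 19.0%. Section 9.6 also omits RT, which 15.4.1 includes, so an RT-related event in a patient who stops early meets the same conflict.

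**3. Grade 3 events due to TMZ or RT alone.** Such an event could be rated unlikely or unrelated to the study drug and not counted. It could also be rated possible in a patient on combined treatment and counted. The specified scale does not separate the components. Section 7.3.1 reports sustained Grade 3 lymphopenia in all patients on 21-day TMZ at 100 mg/m², and this trial targets 50–100 mg/m² on that schedule. The 50 mg/m² starting dose and the clinical-significance filter on laboratory AEs limit the relevance, but the choice may not be minor.

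**4. Reproducing the plan's suspension figures.** Inputs: Table 3 boundary, 20 patients, outcome known at accrual (Section 15.4.2). Let f_n(k) be the probability of k events among n patients with no suspension so far. Then f_n(k) = f_{n-1}(k)(1−p) + f_{n-1}(k−1)p. After each of patients 6 to 20, the probability at or above the boundary moves to suspended.

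| True rate p | Plan's figure | Last row ≥5 (as printed) | Last row ≥6 |
|---|---|---|---|
| 0.10 | 0.034 | 0.059 | 0.037 |
| 0.18 | 0.21 | 0.316 | 0.212 |
| 0.20 | 0.27 | 0.402 | 0.279 |
| 0.25 | 0.46 | 0.611 | 0.469 |
| 0.30 | 0.65 | 0.780 | 0.654 |
| 0.35 | 0.80 | 0.891 | 0.802 |

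The plan's figures fit, approximately, a last row of ≥6 above 14 patients. Table 3 in the available text reads ≥5. This is a separate matter, possibly a fault of text extraction, so both versions are carried forward.

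**5. Illustration of size.** Let u be the share of patients with a Grade 4 event due only to a procedure, independent of other toxicity. The documents give no value, so u is assumed. Then p = 1 − (1 − 0.18)(1 − u):

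- u = 2%: 1 − 0.82 × 0.98 = 0.196
- u = 5%: 1 − 0.82 × 0.95 = 0.221
- u = 10%: 1 − 0.82 × 0.90 = 0.262

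| u | p | P(suspend), last row ≥6 | P(suspend), last row ≥5 |
|---|---|---|---|
| 0 | 18.0% | 0.21 | 0.32 |
| 2% | 19.6% | 0.27 | 0.39 |
| 5% | 22.1% | 0.36 | 0.49 |
| 10% | 26.2% | 0.52 | 0.66 |

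**The case against.** A broad Grade 4 count is a defensible conservative choice for a vaccine not previously used in humans. Surgery follows vaccine #3 closely, and Section 12.8.2 lists both surgery and immune infiltration as causes of edema. In an uncontrolled study, removing events judged solely surgical could remove true vaccine toxicity. Suspension is also temporary, and Section 15.4.2 allows accrual to resume with no protocol change after review. All of this stands. It argues against deleting these events, but not against identifying them.

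One could read the excluded causes in the life-threatening limb as covering Grade 4 too. The wording does not say so, and the list names neither surgery nor leukapheresis.

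The illustration has limits. The 18% covers any Grade 3 or 4 event on TMZ alone, which is not this endpoint. The model also applies u at the six-patient review, which concerns toxicity during the first three vaccinations, before craniotomy.

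A reader might infer four stronger things that the documents do not support:

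- **Every Grade 4 event counts whatever its cause.** Progression-related neurologic events are exempt, and 9.6 requires relatedness below six vaccines.
- **The endpoint runs from consent.** That is the collection window; 15.4.1 states no window. Section 13.1 defines an AE in a subject receiving study drug, and never-vaccinated patients are excluded. Whether a leukapheresis event counts is unclear.
- **RT complications contaminate the rate.** The primary objective covers vaccine with RT, so they are partly intended.
- **Grade 3 events due to TMZ or RT cannot be classified and are lost.** They may be rated possible and counted. The text does not determine which.

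**Conclusion.** The point holds as an ambiguity in the primary variable, and it should be fixed. Three parts rest on the text alone: the Grade 4 limb lacks an attribution test that its neighbours have; 9.6 disagrees with 15.1 and 15.4.2 on relatedness; and the attribution scale covers only the vaccine, although the endpoint and its benchmark involve TMZ and, for the endpoint, RT.

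The size is illustrative. It depends on assumed procedural rates of 2% to 10%, independence, the 18% benchmark, and which last row of Table 3 applies. Under those assumptions the endpoint rate rises by 1.6 to 8.2 percentage points. Suspension probability rises by about 0.06 to 0.30 with the ≥6 row, or 0.07 to 0.34 with the ≥5 row. The effect of the Grade 3 ambiguity cannot be sized, because the documents do not split the 18% by grade. This does not show that the trial is unsafe or that the Grade 4 count must be narrowed.

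**What to change.** 1. On the AE form, record attribution separately for vaccine, TMZ, RT and procedure (surgery or leukapheresis). Derive the Grade 3 limb from the vaccine, TMZ and RT fields. Capture this when the event occurs.
2. Reconcile 9.6 with 15.1 and 15.4.2 on whether an early-stopping patient's event must be related, and to what, including RT. State the start and end of the endpoint window.
3. Keep the conservative Grade 4 count. Report the primary percentage and the Table 3 count both with and without Grade 4 events judged due solely to surgery or leukapheresis.
4. The sponsor should reconcile the Grade 4 and life-threatening limbs. The definition also feeds withdrawal (12.6.1) and replacement (12.6.3), so no rule is proposed here for those.

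The cost is a few AE form fields, short edits to the definition, AE and analysis sections, and one extra row in the safety tables. Attribution remains an investigator judgment, which is why both versions should be shown.
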